4.5.1 Permitted, Restricted, and Prohibited Medications

Prohibitions and restrictions for concomitant medications, as specified in [Appendix H](#) and [Appendix I](#), should be followed between Visit 1 (Screening) and Visit 17/ET. Medications that can prolong QT interval are prohibited (or restricted if approved by the Medical Monitor or appropriate designee) as specified in Appendix H. These appendices do not constitute an exhaustive list and any questions regarding prohibited and restricted medications or the use of medications that could interfere with study conduct should be discussed with the Medical Monitor or appropriate designee.

If a subject is on a restricted or prohibited medication at screening, the medication should be adjusted or discontinued only if it is determined by the Investigator to be clinically appropriate (e.g., if the subject's symptoms are not well-controlled or if the subject cannot tolerate the current medication).

The Investigator may prescribe, adjust, or discontinue appropriate medication to treat or manage AEs. Subjects who require current treatment with a prohibited medication will be withdrawn from the study.

Subjects who are discovered to have previously taken a prohibited medication during the study will be withdrawn from the study unless:

- the prohibited medication has been discontinued AND
- withdrawal from the study presents an unacceptable medical risk to the subject

The justification to allow the subject to remain in the study will be made by the Sponsor/Medical Monitor, with medical input from the Investigator, and will be documented. If the subject is allowed to remain in the study, this will be reported as a major protocol deviation and not a waiver.

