Serotonin antagonists	PROHIBITED 
 • cyproheptadine 	
 • Prohibited throughout the study • Must be discontinued at least 3 weeks prior to the Baseline visit
Antiarrhythmic drugs	PROHIBITED 
 • ajmaline • amakalant, semantilide • amiodarone • bretylium • disopyramide • dofetilide • dronedarone • flecainide • ibutilide • procainamide • propafenone • quinidine • sotalol, d-sotalol 	
 • Prohibited at study entry and throughout the study
Opioids	PROHIBITED 
 • methadone 	
 • Prohibited at study entry and throughout the study

Medication Class	Medication ¹	Prohibition/restrictions
Antimicrobials, antifungals, and antimalarials	PROHIBITED 
 • clarithromycin • erythromycin • levofloxacin • moxifloxacin • pentamidine • roxithromycin 	
 • Prohibited at study entry and throughout the study
	RESTRICTED 
 • arteminol/piperaquine • azithromycin • bedaquiline • ciprofloxacin • gemifloxacin • norfloxacin • ofloxacin • fluconazole • telavancin • telithromycin 	
 • Prohibited at Baseline but may be used during the course of the study to treat a bacterial infection (e.g., urinary tract infection, respiratory infection), post-Baseline at the discretion of the Principal Investigator. • The medications on the left are only allowed under the following conditions: 
 ○ The subject has a Baseline ECG with a QTcF <425 ms IF QRS duration is <120 ms OR ○ The subject has a QTcF <450 ms at Baseline IF QRS duration ≥120 ms

¹ Medications within each class include but are not limited to the examples listed in this table.

Appendix I Prohibited and Restricted Concomitant Medications: Inhibitors and Inducers of Cytochrome P450 Enzyme 3A4

The information presented here is intended to provide guidance and does not constitute an exhaustive list of strong CYP 3A4 enzyme (CYP3A4) inhibitors and inducers. Any questions should be discussed with the Medical Monitor or appropriate designee. Details regarding procedures for subjects who take a prohibited medication during the study are provided in [Section 4.5.1](#).

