The metabolism of pimavanserin is affected by strong CYP3A4 inhibitors, resulting in an increase in maximum plasma concentration (C_{max}) and area under the plasma concentration-time curve (AUC) of approximately 3-fold.

Strong inhibitors of CYP3A4 are to be stopped at least 7 days or 5 half-lives prior to investigational product administration, whichever is longer. Strong inducers of CYP3A4 are to be stopped 30 days or 5 half-lives prior to investigational product administration, whichever is longer.

Moderate inhibitors and inducers of CYP3A4 may be allowed but should be used with caution.

STRONG INHIBITORS
	
grapefruit juice^a boceprevir (Victrelis[®]) clarithromycin (Biaxin[®]) cobicistat (part of Stribild[®]) conivaptan (Vaprisol[®]) fluvoxamine (Luvox[®]) indinavir (Crixivan[®]) itraconazole (Sporanox[®]) ketoconazole (Nizoral[®]) lopinavir and ritonavir (Kaletra[®]) mibefradil (Posicor[®]) nefazodone (Serzone[®]) nelfinavir (Viracept[®]) posaconazole (Noxafil[®]) quinupristin (Synercid[®]) ritonavir (Norvir[®], part of Viekira Pak[™]) saquinavir (Invirase[®]) telaprevir (Incivek[®]) telithromycin (Ketek[®]) voriconazole (Vfend[®])
	
MODERATE INHIBITORS
	
grapefruit juice^a amprenavir (Agenerase[®]) aprepitant (Emend[®]) atazanavir (Reyataz[®]) ciprofloxacin (Cipro[®]) darunavir/ritonavir (Prezista[®]/Ritonavir) diltiazem erythromycin (Erythrocin[®] Lactobionate) fluconazole (Diflucan[®]) fosamprenavir (Lexiva[®]) imatinib (Gleevec[®]) verapamil (Calan[®])

---------------------------------	--	-----------------------------------	--

STRONG INDUCERS
	
avasimibe carbamazepine (Tegreto1®) phenobarbital (Luminal®, Solfoton®) phenytoin (Dilantin®) rifampin (Rifadin®, Rifadin® IV, Rimactane®) St. John's Wort
	
MODERATE INDUCERS
	
bosentan (Tracleer®) efavirenz (Sustiva®) etravirine (Intelence®) modafinil (Provigil®) nafcillin (Unipen®, Nallpen®)

-----------------------------------	---	-------------------------------------	--

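### Appendix H lets sites start telithromycin after Baseline, although Appendix I lists it as a strong CYP3A4 inhibitor

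*Protocol*

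**What the plan says.** **Appendix H, antimicrobials.** Telithromycin is one of ten entries in the restricted row. The rule for that row is "Prohibited at Baseline but may be used during the course of the study to treat a bacterial infection". The decision lies with the principal investigator. The subject's Baseline QTcF must be below 425 ms (QRS under 120 ms) or below 450 ms (QRS 120 ms or more). No condition mentions CYP3A4, and the row does not point to Appendix I.

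**Appendix I.** Telithromycin is in the strong-inhibitor column. On that class the appendix says: "The metabolism of pimavanserin is affected by strong CYP3A4 inhibitors, resulting in an increase in maximum plasma concentration"; the stated size, for Cmax and AUC alike, is about 3-fold. The rule is "Strong inhibitors of CYP3A4 are to be stopped at least 7 days or 5 half-lives prior to investigational product administration". The only allowance is for the weaker tier: "Moderate inhibitors and inducers of CYP3A4 may be allowed but should be used with caution". The appendix describes itself as guidance and its lists as not exhaustive.

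**Section 4.5.1.** The rules in both appendices "should be followed between Visit 1 (Screening) and Visit 17/ET". On QT-prolonging drugs it says: "Medications that can prolong QT interval are prohibited (or restricted if approved by the Medical Monitor or appropriate designee". On consequences it says: "Subjects who require current treatment with a prohibited medication will be withdrawn from the study".

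**Section 5.1.4.** After Week 4 the study drug dose is fixed at 34 mg or 20 mg.

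**The concern.** A site that checks Appendix H for an antibiotic finds telithromycin expressly available and has no evident reason to look further. It could then add a strong inhibitor to a drug for which Section 1.3.1 reports a potential QT risk and a mean prolongation of about 5 to 8 ms at 34 mg, in subjects aged up to 90. Antibiotic need is foreseeable: Section 1.3.2 reports urinary tract infection in 22.2% of the pimavanserin group in the Phase 2 Alzheimer's psychosis study.

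Three features limit what a site can do about the interaction:

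- The dose cannot be reduced after Week 4.
- The QTcF condition is a Baseline value, taken before any interaction.
- The row requires no ECG when the antibiotic starts. Scheduled ECGs after Baseline fall only at Weeks 2, 12, 18, 26 and 38.

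The listing also decides how the subject is handled. Someone who needs a prohibited drug is withdrawn; nothing requires withdrawal for a restricted drug used within its conditions. Two sites could therefore treat the same prescription differently. A withdrawal made on this ground before relapse is an event for the key secondary endpoint (SAP 5.2.4) and a censoring for the primary (SAP 5.2.3).

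**Working it through.** No sample size, power or alpha figure is involved. The check is a comparison of the two lists, followed by some short arithmetic.

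**Step 1: overlap of the lists.** Appendix I names 20 strong inhibitors, 6 strong inducers, 12 moderate inhibitors and 5 moderate inducers. Those also named in Appendix H are:

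| Tier in Appendix I | Prohibited in H | Restricted in H |
|---|---|---|
| Strong inhibitor | clarithromycin, fluvoxamine, nefazodone | telithromycin |
| Strong inducer | carbamazepine, phenytoin | none |
| Moderate inhibitor | erythromycin | ciprofloxacin, fluconazole |
| Moderate inducer | modafinil | none |

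- Drugs in both appendices: 4 + 2 + 3 + 1 = 10.
- Strong agents in both: 4 + 2 = 6, of which H prohibits 3 + 2 = 5 and restricts 1.
- Among strong inhibitors alone, telithromycin is the 1 of 4 not prohibited.

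The nefazodone match reads the spelling *nefazadone* in Appendix H as the same drug. Ciprofloxacin and fluconazole are restricted in H but only moderate in I, so they do not conflict.

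**Step 2: does Appendix I bar use on treatment?** Its express rule is a washout before dosing. The bar on treatment is an inference from three texts. Section 4.5.1 keeps both appendices in force through Visit 17/ET. The title of Appendix I refers to concomitant medications, and its introduction points to the procedure for a prohibited drug taken during the study. The allowance for moderate agents would serve little purpose if strong agents were allowed too.

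**Step 3: fixed-dose period.** Open-label plus double-blind treatment is 12 + 26 = 38 weeks. From Week 4 to Week 38 the dose cannot change: 38 − 4 = 34 weeks. Section 5.1.4 also holds 34 mg for at least the first week, so the period without a permitted change is about 34 + 1 = 35 of 38 weeks. In the double-blind period this matters only for subjects randomized to pimavanserin.

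**Step 4: exposure.** Taking the class figure of 3-fold and assuming exposure proportional to dose, which the documents do not state:

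- 34 mg × 3 = 102 mg equivalent
- 20 mg × 3 = 60 mg equivalent

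The thorough QT study in Section 1.3.1 covered 17 to 68 mg. On these assumptions, exposure at 34 mg would exceed the studied range and exposure at 20 mg would lie within it. No figure specific to telithromycin is given.

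**Step 5: after the correction.** All 6 of the 6 shared strong agents would be prohibited in H, and 10 − 1 = 9 restricted antimicrobials would remain.

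**The case against.** The strongest reply is that the express texts can be reconciled. Appendix I states a washout and calls itself guidance. Appendix H bars the drug at Baseline, which agrees with a washout. Where Appendix H means a ban for the whole study, it says so; Appendix I does not. If the bar on treatment is nevertheless accepted, Section 4.5.1 already applies both appendices together, and a site following both would not use telithromycin. Use is also gated: by a bacterial infection, the investigator's judgement, the Baseline QTcF limits and, for QT-prolonging drugs, Medical Monitor approval under Section 4.5.1.

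Much of this is fair. The bar is inferred, and the gates are real. The QTcF limits are tighter than the general entry limits of 450 and 470 ms. But none of the gates addresses CYP3A4, and the Appendix H row gives the decision to the investigator without mentioning the Medical Monitor. Reading both appendices together resolves the matter only for a site that notices the second listing.

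It can also be said that Appendix H does not follow the tiers of Appendix I, since erythromycin and modafinil are moderate in I and prohibited in H. That weakens the inference that telithromycin was misplaced by accident. Both of those drugs err on the strict side, however, and leave no safety gap.

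Finally, placebo subjects have no continuing pimavanserin dosing to interact with, and study drug can be interrupted or withdrawn (Section 7.2.2.3). These points reduce the number exposed and the harm; they do not remove the inconsistency.

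**Conclusion.** The concern holds, at minor severity. Appendix H expressly allows, on treatment, a drug that Appendix I places in a class it makes no allowance for. It is 1 of the 10 drugs named in both appendices and 1 of the 6 strong agents, and the only one of the 10 for which H is the more permissive list. The pattern suggests a misplaced entry, but the documents do not prove that.

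The conclusion rests on reading Section 4.5.1 as carrying the strong-inhibitor rule through Visit 17/ET. The listing mismatch itself is certain. The clinical size cannot be estimated: the documents give the 3-fold class effect but no telithromycin usage rate and no drug-specific exposure or QT figure, and use may be very rare. Sample size and the primary analysis are not affected.

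**What to change.** 1. In the Appendix H antimicrobials section, move telithromycin from restricted to prohibited, beside clarithromycin.
2. In Appendix I, state that strong CYP3A4 inhibitors are prohibited from washout through Visit 17/ET, and that the stricter listing governs any drug named in both appendices.

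The cost is a two-line appendix correction and a memo to sites. Sites lose one antibiotic option, with nine agents left in the restricted row, and a subject who truly needs telithromycin would be withdrawn under Section 4.5.1.

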Appendix J New York Heart Association Classification of Heart Failure

Class	Patient Symptoms
I	No limitation of physical activity. Ordinary physical activity does not cause undue fatigue, palpitation, dyspnea (shortness of breath).
II	Slight limitation of physical activity. Comfortable at rest. Ordinary physical activity results in fatigue, palpitation, dyspnea (shortness of breath).
III	Marked limitation of physical activity. Comfortable at rest. Less than ordinary activity causes fatigue, palpitation, or dyspnea.
IV	Unable to carry on any physical activity without discomfort. Symptoms of heart failure at rest. If any physical activity is undertaken, discomfort increases.

Source: [American Heart Association](#)

Appendix K Canadian Cardiovascular Society Angina Grading Scale

Grade	Description
I	Ordinary physical activity does not cause angina, such as walking and climbing stairs. Angina with strenuous or rapid or prolonged exertion at work or recreation
II	Slight limitation of ordinary activity. Walking or climbing stairs rapidly, walking uphill, walking or stair climbing after meals, or in cold, or in wind, or under emotional stress, or only during the few hours after awakening. Walking more than two blocks on the level and climbing more than one flight of ordinary stairs at a normal pace and in normal conditions
III	Marked limitation of ordinary physical activity. Walking one or two blocks on the level and climbing one flight of stairs in normal conditions and at normal pace
IV	Inability to carry on any physical activity without discomfort, anginal syndrome may be present at rest

Sources: [Campeau L 1976](#)

Appendix L Predictors Composing the PHASES Aneurysm Rupture Risk Score

PHASES aneurysm risk score	Points
(P) Population	
North American, European (other than Finnish)	0
Japanese	3
Finnish	5
(H) Hypertension	
No	0
Yes	1
(A) Age	
<70 years	0
≥70 years	1
(S) Size of aneurysm	
<7.0 mm	0
7.0-9.9 mm	3
10.0-19.9 mm	6
≥20 mm	10
(E) Earlier SAH from another aneurysm	
No	0
Yes	1
(S) Site of aneurysm	
ICA	0
MCA	2
ACA/Pcom/posterior	4

Source: [Greving et al. 2014](#)

Abbreviations: ACA=anterior cerebral arteries (including the anterior cerebral artery, anterior communicating artery, and pericallosal artery); ICA=internal carotid artery; MCA=middle cerebral artery; Pcom=posterior communicating artery; posterior=posterior circulation (including the vertebral artery, basilar artery, cerebellar arteries, and posterior cerebral artery); SAH=subarachnoid haemorrhage

Note: To calculate the PHASES risk score for an individual, the number of points associated with each indicator can be added up to obtain the total risk score.

Table 1	Schedule of Assessments for Screening and Open-label Period.....	17
Table 2	Schedule of Assessments for Double-blind Period.....	19
Table 3	Analysis Visit Windows for the Open-label Period	32
Table 4	Analysis Visit Windows for the Double-Blind Period	32
Table 5	Criteria for PCI Laboratory Values – Hematology and Chemistry.....	65
Table 6	Criteria for PCI Laboratory Values - Urinalysis	66
Table 7	Criteria for PCI Vital Signs.....	68
Table 8	Criteria for PCI ECG Values.....	71
Table 9	O’Brien-Fleming Stopping Boundary Information	75

LIST OF FIGURES

Figure 1	Schematic of Study Design	14
----------	---------------------------------	----

ABBREVIATIONS

AE	adverse event
ATC	Anatomical Therapeutic Chemical
BMI	body mass index
CI	confidence interval
CGI-I	Clinical Global Impression-Improvement
CGI-S	Clinical Global Impression-Severity
DB	double-blind
DSMB	Data and Safety Monitoring Board
eCRF	electronic case report form
ECG	electrocardiogram
EOT	end-of-treatment
FDA	Food and Drug Administration
FTD	frontotemporal dementia
GCAS	Global Clinician Assessment of Suicidality
IAC	Independent Adjudication Committee
ISG	Independent Statistical Group
ITT	intent-to-treat
KSS	Karolinska Sleepiness Scale
LLOQ	lower limit of quantification
LS	least squares
MedDRA	Medical Dictionary for Regulatory Activities
MMRM	Mixed model repeated measures
MMSE	Mini-Mental State Examination
msec	milliseconds
OL	open-label
PCI	potentially clinically important
PK	pharmacokinetic
QTcF	QT interval corrected for heart rate using Fridericia's formula
SAE	serious adverse event
SAP	statistical analysis plan
SAPS-H+D	Scale for Assessment of Positive Symptoms-Hallucinations + Delusions
SAS [®]	Statistical Analysis System
SD	standard deviation

SE	standard error
SOC	system organ class
TEAE	treatment-emergent adverse event
ZBI	Zarit Burden Interview

1 INTRODUCTION

This statistical analysis plan (SAP) provides a technical and detailed elaboration of the statistical analyses of efficacy and safety data as described in Protocol Amendment 1 dated 16 August 2018. Specifications for tables, figures, and listings are contained in a separate document.

2 STUDY OBJECTIVES AND ENDPOINTS

2.1 Primary Objective

The primary objective is to evaluate relapse prevention in subjects with dementia-related psychosis treated with pimavanserin compared to placebo.

2.1.1 Primary Endpoint

The primary endpoint for this study will be time from randomization to relapse in the double-blind period.

2.2 Key Secondary Objective

The key secondary objective is to evaluate the time to discontinuation of the study for any reason in subjects with dementia-related psychosis treated with pimavanserin compared to placebo.

2.2.1 Key Secondary Endpoint

The key secondary endpoint for this study will be time from randomization to discontinuation from the double-blind period for any reason.

2.3 Exploratory Objectives

The exploratory objectives are to evaluate the benefit of pimavanserin compared to placebo in the following domains in subjects with dementia-related psychosis who have been stabilized on pimavanserin therapy:

- symptoms of hallucinations and delusions
- clinical global impression
- caregiver burden

- daytime sleepiness
- quality of life

2.3.1 Exploratory Endpoints

The exploratory endpoints for this study are as follows:

- Change from double-blind Baseline on the following:
 - Scale for the Assessment of Positive Symptoms-Hallucinations+Delusions (SAPS-H+D) score
 - SAPS Hallucinations domain score
 - SAPS Delusions domain score
 - Clinical Global Impression-Severity (CGI-S)-dementia-related psychosis
 - Zarit Burden Interview (ZBI) score
 - Karolinska Sleepiness Scale (KSS) score
 - EQ-5D-5L score
 - Clinical Global Impression-Improvement (CGI-I)-dementia-related psychosis

2.4 Safety Objective

The safety objective for this study is to evaluate the safety and tolerability of pimavanserin compared to placebo in subjects with dementia-related psychosis who have been stabilized on pimavanserin therapy.

2.4.1 Safety Endpoints

The safety endpoints for this study are as follows:

- Treatment-emergent adverse events (TEAEs)
- Serious adverse events (SAEs)
- Withdrawals due to adverse events (AEs)
- Potentially clinically important changes in other safety assessments
- Global Clinician Assessment of Suicidality (GCAS) score
- Mini-Mental State Examination (MMSE) score
- Extrapyrarnidal Symptom Rating Scale A (ESRS-A) score

2.5 Pharmacokinetic Objectives

The pharmacokinetic (PK) objectives for this study are as follows:

- To characterize the PK of pimavanserin in subjects with dementia-related psychosis
- To assess the pharmacokinetic/pharmacodynamics (PK/PD) relationship with safety and efficacy endpoints in subjects with dementia-related psychosis

2.5.1 Pharmacokinetic Endpoints

The PK endpoints for this study are as follows:

- Plasma concentration of pimavanserin and AC-279
- Pimavanserin PK parameters using a population PK approach
- PK/PD using appropriate PK/PD analysis methods

3 STUDY DESIGN

[figure not shown]
3.1 General Study Design

This is a Phase 3, prospective, double-blind, placebo-controlled, multicenter, relapse prevention study in subjects with dementia-related psychosis. Approximately 95 study sites will participate in this study.

The duration of participation for individual study subjects will be up to 47 weeks, consisting of a screening period of up to 5 weeks; an open-label (OL) period of 12 weeks; a double-blind (DB) period of up to 26 weeks; and an approximately 4-week safety follow-up period.

The study discontinuation date is defined as the day on which the Sponsor notifies sites that the study is ending (for example, in the event of a positive interim analysis or after 75 adjudicated relapse events). The study completion date is defined as the day on which the last subject completes the last scheduled assessment (i.e., safety follow-up). A study schematic is provided in [Figure 1](#).

Figure 1 Schematic of Study Design

Screening Period (3-35 Days)

During the screening period, subjects will be assessed for study eligibility and prohibited medications will be discontinued when medically appropriate. Subjects and partner/caregivers will also receive a standardized psychosocial therapy training.

Investigators should not withdraw a subject's prohibited medication for the purpose of enrolling them into the study. Medications should be discontinued only if it is deemed clinically appropriate to do so.

Open-label Period (12 Weeks)

During the open-label period, eligible subjects will begin receiving pimavanserin 34 mg once daily (QD) beginning at Week 0 (open-label Baseline). Subsequent clinic visits will occur at Weeks 2, 4, 8, and 12. Dose adjustments are permitted at scheduled or unscheduled visits until Week 4. After Week 4, the subject's dose will remain fixed at either 34 mg or 20 mg once daily.

To enter the double-blind period, eligible subjects must meet the following response criteria at Weeks 8 and 12:

- Subject experiences a $\geq 30\%$ reduction (improvement) from Week 0 (open-label Baseline) on the Scale for the Assessment of Positive Symptoms – Hallucinations + Delusions (SAPS-H+D) Total Score AND

- Subject has a Clinical Global Impression – Improvement (CGI-I) score of 1 (very much improved) or 2 (much improved), relative to Week 0 (open-label Baseline)

A subject who does not meet response criteria at Weeks 8 and 12 will be withdrawn from study drug and enter the safety follow-up period of the study.

Pharmacokinetic samples will be collected at Weeks 0, 8, and 12. Pharmacokinetic samples will also be collected, if possible, at any ET visit or the visit immediately following any SAE or following an AE leading to discontinuation.

Double-blind Period (up to 26 Weeks)

Randomization will occur at the double-blind Baseline visit (Week 12). Subjects will be randomly assigned 1:1 to continue their pimavanserin dose (34 mg or 20 mg) or matching placebo.

The protocol-defined relapse criteria for dementia-related psychosis are designed to identify subjects with an impending relapse or relapse of psychosis:

- Subject experiences a $\geq 30\%$ increase (worsening) from Week 12 (double-blind Baseline) on the SAPS-H+D Total Score AND has a CGI-I score of 6 (much worse) or 7 (very much worse), relative to the double-blind Baseline; OR
- Subject is treated with an antipsychotic (other than pimavanserin) for dementia-related delusions and/or hallucinations; OR
- Subject stops study drug or withdraws from study for lack of efficacy, (as reported by the subject or study partner/caregiver) or the Investigator discontinues study drug due to lack of efficacy; OR
- Subject is hospitalized for worsening dementia-related psychosis

Relapse criteria will be assessed weekly for the first 2 weeks after randomization (Weeks 13 and 14), every 2 weeks until Week 26, and every 4 weeks through Week 38. Relapse criteria may also be evaluated at unscheduled visits. Any subject who meets any of the relapse criteria after randomization will be withdrawn from study drug and enter the safety follow-up period of the study.

All subjects who discontinue the study between randomization and Week 38 should complete an ET visit, if possible. The Independent Adjudication Committee (IAC) will adjudicate early termination and relapse events that occurred before the study discontinuation date. Early termination and relapse events that occur in the double-blind period after the study discontinuation date will not be adjudicated.

An interim and final analysis will be planned after 38 and 75 adjudicated relapse events have occurred, respectively. The study may be terminated early if the interim analysis results establish the efficacy and safety of pimavanserin for the treatment of hallucinations and delusions associated with dementia-related psychosis.

The Data Safety Monitoring Board (DSMB) will monitor, review, and evaluate the unblinded safety data on a periodic basis. In addition, the DSMB will review the results of the pre-planned unblinded interim analysis conducted by the Independent Statistical Group.

Pharmacokinetic samples will be collected at Weeks 13, 22, and 38/EOT. Pharmacokinetic samples will also be collected, if possible, at any ET visit or the visit immediately following any SAE or following an AE leading to discontinuation.

Safety Follow-up Period (Approximately 4 Weeks)

Approximately 4 weeks after the last dose of study drug, subjects will have a safety follow-up telephone call visit.

The Sponsor will provide investigative sites with 3 months of after-study assistance to transition subjects to standard of care therapy after their participation in the study.

Table 1 Schedule of Assessments for Screening and Open-label Period

	Screening	Open-label Period				
Visit week	-5 to 0	0	2	4	8	12 ^a
Allowable visit window (# days)			±3	±3	±3	+7
Visit Number	1	2	3	4	5	6
Informed consent	X					
Inclusion/exclusion criteria assessment	X	X				
Medical history and demographics	X					
Mini-Mental State Examination	X	X	X	X	X	X
MRI or CT ^b	X					
Psychosocial therapy training	X					
Physical and neurological examinations	X	X				X
Vital signs and weight	X	X	X	X	X	X
Height	X					
12-lead electrocardiogram ^c	X	X	X			X
Clinical laboratory tests	X	X				X
Pregnancy test ^d	X	X				X
SAPS-H+D	X	X	X	X	X	X
Clinical Global Impression-Improvement ^e			X	X	X	X
Clinical Global Impression-Severity	X	X	X	X	X	X
Zarit Burden Interview ^f		X				X
Karolinska Sleepiness Scale		X				X
EQ-5D-5L		X				X
Assessment for response criteria					X	X
Assessment for concomitant medications	X	X	X	X	X	X
Global Clinician Assessment of Suicidality	X	X	X	X	X	X
Extrapyramidal Symptom Rating Scale A		X				X
Assessment for adverse events	X	X	X	X	X	X
Pharmacokinetic sample collection ^g		X			X	X
Pharmacogenomic sample collection ^h		X				
Drug dispensation		X	X	X	X	X ⁱ
Drug return and accountability			X	X	X	X
Randomization						X

Footnotes for Table 1 on next page

Abbreviations: CT=computed tomography; MRI=magnetic resonance imaging;
SAPS-H+D=Scale for the Assessment of Positive Symptoms, Hallucinations and Delusions
subscales

Note: All efforts should be made to complete visits in a single day. In the event of a split visit, the CGI-S/CGI-I and the SAPS H+D must be completed on the same day (pertinent for all visits).

Note: When a subject is found to be appropriate for discontinuation from the trial, the visit during which this is determined should immediately be converted to an ET visit (as described in [Table 2](#)) and all procedures and assessments done at the ET visit (Week 38/EOT; Visit 17/EOT) should be completed (additional details provided in Section 4.4 of the protocol). Safety follow-up should be completed as scheduled.

For additional details on study procedures, see Section 6 of the protocol.

- a Visit 6 (Week 12) will serve as both the final visit of the open-label period and the Baseline visit of the double-blind period (Table 2).
- b A non-contrast brain MRI or non-contrast head CT will be completed if the subject has not had a CT or MRI scan completed (a) within the past 3 years AND (b) during or subsequent to the onset of dementia.
- c The ECG will be completed in triplicate at Visit 1 (Screening). A single ECG will be completed at all other visits.
- d A pregnancy test (serum at Visit 1 and urine at all other visits) is only required for women of child-bearing potential. If urine cannot be obtained in women of child-bearing potential, a serum pregnancy test should be done in its place.
- e The CGI-I should be scored relative to Visit 2, the subject's open-label Baseline.
- f The ZBI should only be administered to study partners/caregivers who are family members.
- g Pharmacokinetic samples will also be collected, if possible, at any ET visit (Table 2) or the visit immediately following any SAE or following an AE leading to discontinuation.
- h A separate informed consent (and assent, if applicable) must be given for the pharmacogenomic component of the study. This consent may be obtained at any time during the study. If informed consent is given in time for sample collection at Visit 2, a pre-dose sample should be collected at Visit 2. If informed consent for pharmacogenomics is not given in time for sample collection at Visit 2, a sample may be collected any time after informed consent for pharmacogenomics is given.
- i Blinded study drug will be dispensed after randomization at Visit 6 (Week 12).

Table 2 Schedule of Assessments for Double-blind Period

Visit week	13	14	16	18	20	22	24	26	30	34	38/EOT	42
Allowable visit window (# days)	±3	±3	±3	±3	±3	±3	±3	±3	±7	±7	+7	+3
Visit Number	7	8	9	10	11	12	13	14	15	16	17/ET	18
Visit Type (Clinic [C] or Telephone [T])	C	C	C	C	T	C	T	C	C	C	C	T
Mini-Mental State Examination	X	X	X	X		X		X	X	X	X	
Physical and neurological examinations						X					X	
Vital signs and weight	X	X	X	X		X		X	X	X	X	
12-lead electrocardiogram				X				X			X	
Clinical laboratory tests				X				X			X	
Pregnancy test ^a								X			X	
SAPS-H+D	X	X	X	X		X		X	X	X	X	
Clinical Global Impression-Improvement ^b	X	X	X	X		X		X	X	X	X	
Clinical Global Impression-Severity	X	X	X	X		X		X	X	X	X	
Zarit Burden Interview ^c				X				X			X	
Karolinska Sleepiness Scale				X				X			X	
EQ-5D-5L				X				X			X	
Assessment for protocol-defined relapse criteria	X	X	X	X	X	X	X	X	X	X	X	
Assessment for concomitant medications	X	X	X	X	X	X	X	X	X	X	X	X
Global Clinician Assessment of Suicidality	X	X	X	X	X	X	X	X	X	X	X	
Extrapyramidal Symptom Rating Scale A	X	X	X	X		X		X	X	X	X	
Assessment for adverse events	X	X	X	X	X	X	X	X	X	X	X	X
Pharmacokinetic sample collection ^d	X					X					X	
Drug dispensation		X	X	X		X		X	X	X		
Drug return and accountability	X ^e	X	X	X		X		X	X	X	X	

Footnotes for Table 2 on next page

Abbreviations: EOT=end-of-treatment; ET=early termination; SAPS-H+D=Scale for the Assessment of Positive Symptoms, Hallucinations and Delusions subscales

For additional details on study procedures, see Section 6 of the protocol.

Note: All efforts should be made to complete visits in a single day. In the event of a split visit, the CGI-S/CGI-I and the SAPS H+D must be completed on the same day (pertinent for all visits).

Note: When a subject is found to be appropriate for discontinuation from the trial, the visit during which this is determined should immediately be converted to an ET visit (as described in [Table 2](#)) and all procedures and assessments done at the ET visit (Week 38/EOT; Visit 17/EOT) should be completed (additional details provided in Section 4.4 of the protocol). Safety follow-up should be completed as scheduled.

- ^a A urine pregnancy test is only required for women of child-bearing potential. If urine cannot be obtained in women of child-bearing potential, a serum pregnancy test should be done in its place
- ^b The CGI-I should be scored relative to Visit 6 (Week12), the subject's double-blind Baseline.
- ^c The ZBI should only be administered to study partners/caregivers who are family members.
- ^d Pharmacokinetic samples will also be collected, if possible, at the visit immediately following any SAE or following an AE leading to discontinuation.
- ^e Only drug accountability will be completed at this visit.

